x. Participation in FeetMe® and PAMSys subsets are optional, but informed consent for these are part of the main informed consent. The use of the sensors does not apply to a patient who scores 4 on UMSARS Part I item 7 (walking) or if the patient is wheelchair bound for unrelated disorders. This needs to be evaluated at each visit, where the sensors are to be dispensed.

Visit Name	Base line - IMP	IMP	IMP	IMP	IMP	IMP	IMP	IMP	IMP	IMP	IMP	IMP	End of Ope n- La- bel Trea tmen t	Wit hdra wal ^a	Safet Y Fol- low- up ^b
Visit Number	1E	2E	3E	4E	5E	6E	7E	8E	9E	10E	11E	12E	13E	WD	SFU- E
Week ^c	0E	4E	8E	12E	16E	20E	24E	28E	32E	36E	40E	44E	48E		64E
Visit Window ^d (days rela- tive to nominal visit)		±3	±3	±3	±3	±3	±3	±3	±3	±3	±3	±3	±3	-	±7
Signed informed consent	√														
Efficacy Assessments															1
UMSARS	√ e			√			√			√			√	$\underline{}$	
CGI-S	\sqrt{e}								i I				$\overline{\mathbf{A}}$		
PGI-S	√e			√	⊢ 		√	╊ ━ ━ ÷ ┃	⊨	√	┝ ━ ━ ▪ 		√	$\underline{}$	•
SE-ADL	\sqrt{e}						√		 		· '		$\underline{}$	$\underline{}$	
EQ-5D-5L	√ e				 !		√	r : I	· 	r — — ·	r — — · !		$\underline{}$	$\underline{}$	
MRI scans: vMRI ^f	√e,g								• ·				$\underline{\checkmark}$	$\overline{}$	
Blood sampling for NfL	√						√			 			√	$\underline{}$	
Pharmacokinetic Assessme	ents														-
Blood sampling for IMP quantification	√ e						√			1	1		√	$\underline{}$	√
Pharmacodynamic Assess	nents														
Blood sampling for α- synuclein	√ e						√						√	$\underline{}$	√
Safety Assessments															
Adverse events	√	√	√	√	√	√	√	√	√	√	√	√	√	√	√

Table 2 Optional Open-label Long-term Extension Treatment Period

Study 18331A - Statistical Analysis Plan

Blood and urine sampling	√e	Г I	Г — — I		r			T I	·	r	F I	T I	$\overline{}$	$\underline{}$	i – – 1 1 – 1
tor clinical safety labora- tory tests	I I	1 1	I I		1	8	1 1	I I	1	1	1 1	I I	I I	I I	1 I 1 I
Vital signs ^h	√	√	√	√	√	$\underline{}$	√	√	√	√	√	√	√	√	* 4 1 1
Examinations ⁱ (physical, neurological)	√e	 	 			 	√			• = = · 	· 	+ · 	√	√	
C-SSRS since last visit	√e	√	√						√	√	√	√	_√	√	_√
Biobanking		•													
Blood sampling for ADA	√e	 					√					1	√	√	√
Other Study Procedures a	Other Study Procedures and Assessments														
IMP administration ^h	$\underline{}$	√	√	$\underline{}$				√	$\overline{}$	$\overline{}$	√		i I	i I	i I I
Concomitant medication	$\underline{}$	√	√	√	$\underline{}$	$\underline{}$	√	√	√	$\underline{}$	√	$\underline{}$	√	√	√
Urine pregnancy test ^j		_√	_√	√	√	$\underline{}$	_√		√	√	√	√	√	_√	·
ADA = Anti-Drug Antibo	ADA = Anti-Drug Antibody; CGI-S = Clinical Global Impression – Severity of Illness; C-SSRS = Columbia-														

Suicide Severity Rating Scale; EQ-5D-5L = Euroqol 5 Dimensions-5 Levels; IMP = investigational medicinal product; PGI-S = Patient Global Impression-Severity of Illness; SE-ADL: Schwab & England Activities of Daily Living; SFU-E = Safety Follow-up OLE; UMSARS = Unified Multiple System Atrophy Rating Scale; vMRI = volumetric magnetic resonance imaging; WD = withdrawal

a Participants who withdraw, except for those who withdraw their consent, will be asked to attend a Withdrawal Visit as soon as possible.

b The Safety Follow-up Visit will take place 16 weeks after Visit 13E / 20 weeks after last IMP administration in case of withdrawal (follow-up of adverse events on-going at EoT or withdrawal, and new AEs and SAEs).

b All assessments may be completed over a maximum of 2 days (except for MRI, see footnote e); if so, the first day is considered the "visit" day according to the schedule and at IMP visits, IMP must be registered in IRT and administered on the second day.

d If the date of a visit does not conform to the schedule, subsequent visits should be planned to maintain the visit schedule relative to Visit 1E. o

e Only applicable for patients who enter the OLE more than 1 week later as the EoT Visit in the double-blind treatment period.

f MRI scan can be performed any day within the Visit Window. Date of MRI scan will not define Day 1 or Day 2 of a visit and will not be regarded as a separate visit.

g MRI scanning only to be performed as Visit 1E if not performed within the last 8 weeks.

h Blood pressure and pulse will be measured immediately prior to IMP administration and patients will be monitored after IMP administration for immediate drug reactions for a minimum of 2 hours with vital signs taken every 30 minutes (±5 minutes) or until stable, whichever is later.

i Including recording of use of feeding tube and/or wheelchair.

j Only for women of childbearing potential. If positive, confirm with serum pregnancy test.

Appendix V PCS Criteria

Study 18331A – Statistical Analysis Plan

Page 78 of 96

PCS Criteria

Laboratory Test	CDISC Torm	Unit	PCSLow	PCS High
		UIII	I CO LUW	i Co mgi
Haematology / Coagulation				
B-haemoglobin	HGB	g/L	\leq 95 (women)	\geq 165 (women)
-		-	\leq 115 (men)	≥185 (men)
B-erythrocytes (red cell count)	RBC	x 10E12/L	\leq 3.5 (women)	\geq 6.0 (women)
			\leq 3.8 (men)	\geq 7.0 (men)
B-haematocrit (packed cell	HCT	V/V	\leq 0.32 (women)	\geq 0.50 (women)
volume)				
			\leq 0.37 (men)	\geq 0.55 (men)
B-MCV (mean cell volume)	MCV	fL	\leq 0.8 x LLN	\geq 1.2 x ULN
B-total leucocyte (white cell count)	WBC	x 10E9/L	≤ 2.8	≥16
B-neutrophils/leucocytes	NEUTLE	%	≤ 20	≥85
B-eosinophils/leucocytes	EOSLE	%		≥ 10
B-basophils/leucocytes	BASOLE	%		≥ 10
B-lymphocytes/leucocytes	LYMLE	%	≤ 10	\geq 75
B-monocytes/leucocytes	MONOLE	%		≥15
B-thrombocytes (platelet count)	PLAT	x 10E9/L	\leq 75	≥ 600
P-INR (prothrombin ratio)	INR	Ratio		≥ 2.0
B-prothrombin time	PT	Sec		≥ 18
Liver				
S-aspartate aminotransferase	AST	U/L		\geq 3 × ULN
S-alanine aminotransferase	ALT	U/L		\geq 3 × ULN
S-bilirubin	BILI	µmol/L		\geq 34
S-bilirubin, direct	BILDIR	µmol/L		≥12
S-bilirubin, indirect	BILIND	µmol/L		≥22
S-alkaline phosphatase	ALP	U/L		\geq 3 × ULN
S-gamma glutamyl transferase	GGT	U/L		\geq 200
S-alpha-glutathione S-transferase (alpha-GST)	GSTAL	μg/L		≥20
Kidney				
S-creatinine	CREAT	µmol/L		\geq 1.5 x ULN
B-urea nitrogen (BUN)	BUN	mmol/L		≥11
S-uric acid (urate)	URATE	µmol/L		\geq 510 (women)
				≥ 630 (men)
Electrolytes				
S-sodium (natrium)	SODIUM	mmol/L	≤ 125	≥155
S-potassium (kalium)	К	mmol/L	≤ 3 .0	≥ 6.0

Table 3 PCS Criteria for Clinical Safety Laboratory Tests

Study 18331A – Statistical Analysis Plan

Page 79 of 96

Laboratory Test	CDISC Term	Unit	PCS Low	PCS High
S-calcium	СА	mmol/L	< 1.8	≥ 3.0
S-chloride	CL	mmol/L	≤ 90	_ ≥117
S-magnesium	MG	mmol/L	≤ 0.6	≥ 1.3
S-phosphate (phosphorus,	PHOS	mmol/L	≤ 0.65	≥ 1.95
(inorganic)				
S-bicarbonate	BICARB	mmol/L	≤ 12	≥38
Endocrine / Metabolic				
B-glucose, non-fasting/unknown	GLUC	mmol/L	≤ 3.4	≥ 9.4
B-glucose, fasting	GLUC	mmol/L	≤ 3.0	≥ 6.0
S-glucose, non-fasting/unknown	GLUC	mmol/L	≤ 3.9	≥11.1
S-glucose, fasting	GLUC	mmol/L	≤ 3.5	≥ 7.0
B-glycosylated haemoglobin, fasting	HBA1C	Hb fract.		≥ 0.065
S-prolactin	PROLCTN	mIU/L		≥1350
S-thyrotropin/TSH	TSH	mIU/L	≤ 0.3	≥ 5.5
S-protein (total)	PROT	g/L	\leq 45	\geq 95
S-albumin	ALB	g/L	≤27	
Lipids				
S-cholesterol total, non- fasting/unknown	CHOL	mmol/L		≥ 7.8
S-cholesterol total, fasting	CHOL	mmol/L		≥ 6.2
S-triglycerides, non- fasting/unknown	TRIG	mmol/L		≥ 5.65
S-triglycerides, fasting	TRIG	mmol/L		≥4.2
S-LDL cholesterol, non- fasting/unknown	LDL	mmol/L		≥ 5.3
S-LDL cholesterol, fasting	LDL	mmol/L		\geq 4.9
S-HDL cholesterol, non- fasting/unknown	HDL	mmol/L	≤ 0.8	
S-HDL cholesterol, fasting	HDL	mmol/L	≤ 0.9	
Cardiac/Skeletal/Muscle				
S-creatine kinase (total)	СК	U/L		\geq 400 (women)
				≥ 750 (men)
S-creatine kinase MB isoenzyme	CKMB	µg/L		\geq 8.5 or
	CKMBCK	%		\geq 3.5% of total CK
S-lactate dehydrogenase (total)	LDH	IU/L		\geq 750
S-troponin I	TROPONI	µg/L		≥1.5
S-troponin T	TROPONT	μg/L		≥ 0.4
Infection				
S-C-reactive protein	CRP	mg/L		≥25
S-globulin (total)	GLOBUL	g/L	≤15	≥ 55
Urine				

Page 80 of 96

Laboratory Test	CDISC Term	Unit	PCS Low	PCS High
Urinary pH	PH		≤ 4	≥9

S=serum; B=whole blood; U=urine

Table 4	PCS Criteria for Vital Signs, Weight/BMI, and Waist Circumference
---------	-------------------------------------------------------------------

Variable	CDISC Term	Unit	PCS Low	PCS High
Waist circumference	WSTCIR	Cm	decrease $\geq 7\%$	increase $\geq 7\%$
Weight	WEIGHT	Kg	decrease $\geq 7\%$	increase $\geq 7\%$
Body Mass Index	BMI	kg/m2	decrease $\geq 7\%$	increase $\geq 7\%$
Pulse rate, supine/sitting/unknown	PULSE	beats/min	< 50 and decrease ≥ 15	\geq 120 and increase \geq 15
Diastolic blood pressure, supine/sitting/unknown	DIABP	mmHg	≤ 50 and decrease ≥ 15	≥ 105 and increase ≥ 15
Systolic blood pressure, supine/sitting/unknown	SYSBP	mmHg	\leq 90 and decrease \geq 20	≥ 180 and increase ≥ 20
Orthostatic systolic blood pressure	OBP	mmHg	≤ - 30	
Orthostatic pulse rate	OPR	beats/min		≥ 20
Temperature	TEMP	°C	decrease ≥ 2	\geq 38.3 and increase \geq 2

Increase/decrease is relative to the baseline value.

Table 5PCS Criteria for ECG Parameters

ECG Parameter	CDISC Term	Unit	PCS Low	PCS High
Absolute Time Interval				
PR interval	PRAG	Msec		≥ 260
QRS interval	QRSAG	Msec		≥150
QT interval	QTAG	Msec		\geq 500
Derived Time Interval				
Heart rate	EGHRMN	beats/min	< 50 and	\geq 120 and
			decrease ≥ 15	increase ≥ 15
QTcB interval	QTCBAG	Msec	< 300	> 500 or
				increase > 60
QTcF interval	QTCFAG	Msec	< 300	> 500 or
				increase > 60

Increase/decrease is relative to the baseline value.

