# 10.6.3 Vital Signs

The investigator may appoint a designee to measure vital signs, provided this is permitted according to local regulations and provided the investigator has trained the designee how to measure vital signs. The investigator must take responsibility for reviewing the findings.

Pulse rate and blood pressure will be measured using a standard digital meter in either supine or sitting position immediately prior to start of IMP administration.

Blood pressure and pulse will be measured immediately prior to IMP administration and patients will be monitored immediately after IMP administration inclusive of saline flush ( $\pm 5$  minutes) for immediate drug reactions for a minimum of 2 hours with vital signs taken at the end of the saline flush and then every 30 minutes ( $\pm 5$  minutes) from the end of the saline flush or until stable, whichever is later (applicable only through Visit 12E).

Beginning at Visit 13E, blood pressure and pulse will only be measured immediately prior to and immediately after IMP administration, inclusive of the saline flush (±5 minutes).

Any out-of-range vital sign considered clinically significant by the investigator must be recorded as an adverse event on an *Adverse Event Form* as according to section 11.1.1.

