#### Anaphylaxis is highly likely when any $\underline{1}$ of the following 3 criteria are fulfilled:

- Acute onset of an illness (minutes to several hours) with involvement of the skin, mucosal tissue, or both (eg, generalized hives, pruritus or flushing, swollen lips-tongue-uvula)
   AND AT LEAST 1 OF THE FOLLOWING:
- a. Respiratory compromise (eg, dyspnea, wheeze-bronchospasm, stridor, reduced PEF, hypoxemia)
- b. Reduced BP or associated symptoms of end-organ dysfunction (eg, hypotonia [collapse], syncope, incontinence)
- 2. Two or more of the following that occur rapidly after exposure to a likely allergen for that patient (minutes to several hours):
- a. Involvement of the skin-mucosal tissue (eg, generalized hives, itch-flush, swollen lips-tongueuvula)
- Respiratory compromise (eg, dyspnea, wheeze-bronchospasm, stridor, reduced PEF, hypoxemia)
- c. Reduced BP or associated symptoms (eg, hypotonia [collapse], syncope, incontinence)
- d. Persistent gastrointestinal symptoms (eg, crampy abdominal pain, vomiting)
- 3. Reduced BP after exposure to known allergen for that patient (minutes to several hours):
- a. Infants and children: low systolic BP (age specific) or greater than 30% decrease in systolic BP\*
- b. Adults: systolic BP of less than 90 mm Hg or greater than 30% decrease from that person's baseline

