3.1 Definition of Baseline

3.1.1 Double Blind Period

The baseline value for the DBP is the value captured at the Baseline Visit (week 0). In case an assessment has not been performed at the Week 0 Baseline visit or the Week 0 value is missing or invalid, the value from the last completed pre-IMP assessment will be used as baseline.

The screening visit takes place approx. 6 weeks prior and the randomisation visit approx. 2 weeks prior the baseline visit.

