3.1.2 Open-label Extension Period

The baseline value for patients who enter the OLE and who have the first visit of the OLE at the same day of the EoTDBP Visit or up to 7 days after the EoTDBP, clinical assessments performed at the EoTBDP Visit will serve as the baseline value for the OLE. For patients entering OLE >7 days after EoTDBP, the OLE baseline value is the value captured at the dedicated Visit 1E.

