16.2 General Methodology for Other safety Data

Unless otherwise specified, tables, graphs, and listings will be based on the APTS.

All tables and graphs will be presented by treatment group.

The denominators for the summaries of a given variable will be based on the number of patients with non-missing values at a given visit or during the assessment period.

Descriptive statistics for the safety variables, both absolute values and changes from baseline, will be presented by visit, separately for each period.

The number and percentage of patients with at least one PCS value at any post-baseline assessment time point will be summarized by variable, separately for each period. All available assessments in each period will be included in the evaluation of PCS values.

For patients with post-baseline PCS values, listings will be provided including all the values for those patients for the variable, with flagging of PCS values and out-of-reference-range values.

For vital signs being measures multiple time during a visit values will be presented graphically within visit over time, where the position will be indicated.

All the adverse events in patients with post-baseline PCS values will be listed by treatment group and patient screening number; the listing will include the PCS value, the assessment date, the change from baseline in PCS value, the preferred term for the adverse event, and start date and stop date of the adverse event. The PCS values and adverse events will be listed in chronological order according to assessment date and the start date of the adverse event

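### The PCS counts for blood pressure and pulse cannot separate drift since baseline from an infusion effect, because the same-visit pre-infusion reading enters no numerical summary

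*SAP*

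**What the plan says.** Table 4 in SAP Appendix V sets two-part criteria. Low systolic pressure needs a value of 90 mmHg or less and a fall of at least 20; low diastolic pressure is "≤ 50 and decrease ≥ 15"; low pulse needs a value under 50 with a fall of at least 15. The footnote reads "Increase/decrease is relative to the baseline value".

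SAP 3.1.1 takes the double-blind baseline from the Week 0 visit. SAP 3.1.2 sets a separate extension baseline: the end-of-treatment value of the double-blind period if entry is within 7 days, and otherwise "For patients entering OLE >7 days after EoTDBP, the OLE baseline value is the value captured at the dedicated Visit 1E".

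Protocol 10.6.3 states "Blood pressure and pulse will be measured immediately prior to IMP administration", followed by readings every 30 minutes for at least 2 hours to look for immediate drug reactions. From Visit 13E this reduces to one reading just before and one just after.

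SAP 16.2 puts all available assessments in a period into the PCS evaluation and counts patients with at least one PCS value. For vital signs measured repeatedly during a visit, "values will be presented graphically within visit over time". Neither document specifies a numerical summary of change from the pre-infusion reading.

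**The concern.** The pre-infusion reading is each infusion's own control, and it is collected for that purpose. The PCS tables compare the post-infusion value with a reading that may be more than a year old. MSA involves autonomic failure and is progressive, and the protocol allows symptomatic treatment to be started or changed, so resting pressure and pulse may move over 48 to 72 weeks for reasons unrelated to the infusion. A low flag can then arise when the infusion changed nothing, and a clear drop within one visit can go unflagged. Protocol 2.3.1 names infusion-related reactions as a potential risk of the class. A reader who turns to the PCS table for a by-arm view of that risk would not get one.

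**Working it through.** There is no stated figure to reproduce, so I applied the written systolic rule and then sized it under assumptions.

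**Rule.** PCS low if post ≤ 90 and (reference − post) ≥ 20.

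| Week 0 | Pre-infusion | Post-infusion | Change from Week 0 | Change within visit | PCS, Week 0 reference | PCS, pre-infusion reference |
|---|---|---|---|---|---|---|
| 140 | 95 | 90 | −50 | −5 | yes | no |
| 104 | 128 | 86 | −18 | −42 | no | yes |
| 150 | 150 | 95 | −55 | −55 | no | no |

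Row 1 is drift counted as PCS. Row 2 is a 33% within-visit fall (42/128) that is not counted. Row 3 fails the absolute limit, and changing the reference does not alter that.

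**When a drop can be missed.** If post ≤ 90, the change part fails only when Week 0 < post + 20, so Week 0 must be below 110 mmHg. In the same way the bound is 65 mmHg for diastolic pressure (50 + 15) and 65 beats/min for pulse.

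**Opportunities.** Dosing every 4 weeks from Week 0 to Week 44 gives 12 infusions, and to Week 68 gives 18. Four readings in 2 hours (120/30) over the 17 later infusions give 17 × 4 = 68 post-infusion readings for a patient who completes 72 weeks. All of them feed an at-least-one count.

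**Size per reading (assumed inputs).** Let m be mean systolic pressure, S the visit-to-visit SD, d the drift and r the infusion drop. Week 0 = m + N(0, S²). The visit level is V = m − d + N(0, S²). Pre = V + N(0, 5²) and post = V − r + N(0, 5²). Simulated results:

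| m, S | Flagged, d = 20, r = 0: Week 0 reference | Same: pre-infusion reference | Missed by Week 0 reference, r = 25: d = 0 | Same: d = 20 |
|---|---|---|---|---|
| 125, 10 | 8.7% | 0.08% | 2.6% | 1.0% |
| 125, 15 | 15.8% | 0.09% | 6.8% | 3.7% |
| 120, 10 | 17.2% | 0.13% | 6.1% | 1.8% |
| 120, 15 | 23.2% | 0.12% | 10.7% | 5.4% |

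The missed share is taken among readings that meet the rule against the pre-infusion value. At m = 110 with no drift it is 18% (S = 10) to 21% (S = 15).

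**Size per patient (second set of assumptions).** With mean 130, between-patient SD 18, visit SD 10, reading SD 6, 17 later infusions with four readings each and no infusion effect, the share of patients with at least one low flag is:

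- no drift: 16% (Week 0 reference) against 4% (pre-infusion reference)
- drift −10 mmHg: 28% against 7%
- drift −20 mmHg: 45% against 10%

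Under this model, 93% to 95% of visits flagged by the Week 0 rule show no within-visit fall of 20 mmHg. With a 25 mmHg infusion drop, the Week 0 rule misses 13%, 7% and 4% of qualifying visits at drifts of 0, −10 and −20.

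**The case against.** The strongest reply is that PCS is a general safety screen. The safety endpoint is change from baseline, Table 4 holds the sponsor's standard criteria (SAP 16.4), and a systolic pressure of 90 after a 50 mmHg fall since Week 0 deserves a flag whatever its cause. This stands, and it is a good reason not to re-base the table.

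A reader might infer that infusion reactions would go unseen. The documents do not support that. Protocol 10.6.3 requires clinically significant vital signs to be recorded as adverse events. The Hypersensitivity Form captures acute hypotension with its readings. SAP 16.1.10 and 16.1.11 summarise infusion interruptions, rate reductions and hypersensitivity events. Within-visit readings are plotted. Two limits remain: adverse event capture depends on the investigator's judgement, and the PCS listings cover only patients already flagged.

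A reader might also infer that a drug that slows progression would leave placebo with more low flags and so hide hypotension on the drug. That is speculative. Drift affects both randomised arms, no test on PCS counts is planned, and the documents give no estimate of drift in resting pressure. Dilution of the comparison is the safer conclusion; in the extension, where every patient receives the drug, there is no control arm to separate the two.

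Nor does Protocol Appendix III supply the missing rule. Its wording is "Adults: systolic BP of less than 90 mm Hg or greater than 30% decrease from" the person's own baseline, not the pre-infusion value, and it belongs to a clinical definition of anaphylaxis after exposure to a known allergen. A stand-alone limit of systolic pressure below 90 would also flag 9% to 26% of readings in the no-effect, 20 mmHg drift scenarios above, which brings the same problem back.

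**Conclusion.** The point holds for the PCS table, at every double-blind infusion after the first and at later infusions in the extension. At the first double-blind infusion the reference already comes from the same visit. Loss of specificity is the larger effect: about 9% to 23% of readings flagged with no infusion effect and a 20 mmHg drift, against about 0.1% with the pre-infusion reference. Missed drops are fewer, about 1% to 11% at mean systolic pressure 120 to 125. The figure of up to about 21% needs a mean of 110, close to the bound at which misses become possible. All of these rest on assumed SDs, drift and drop; only the direction and the 110 mmHg bound follow from the documents. This is a cheap improvement to a descriptive safety output, not a fault that leaves infusion reactions unreported.

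**What to change.** Keep the baseline-referenced PCS table unchanged. In SAP 16.2 and 16.4:

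- Add a by-arm, by-visit summary of change in blood pressure and pulse from the same visit's pre-infusion reading.
- Add a count of patients who meet the existing Table 4 limits with that reading as the reference.
- Exempt these readings from the SAP 24.2 rule that only the last assessment of a day is valid. Applied literally, it would remove the pre-infusion and early post-infusion values, and it also conflicts with the use of all available assessments in SAP 16.2.
- State in SAP 3.1.1 that the pre-infusion reading is the Week 0 baseline, since Week 0 has readings both before and after the infusion.

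Do not add a stand-alone category for systolic pressure below 90, and do not attribute the new count to Appendix III. The readings are already collected and entered in the eCRF (Protocol 7.2), so the cost is SAP wording, one derived variable and one extra table. Large drops that end above the absolute limits will still not be counted as PCS, but they will appear in the change summary.

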Appendix VI

Definition of Hypersensitivity related reactions

H. Lundbeck A/S Confidential

Definition of Hypersensitivity related reactions

Type I hypersensitivity reaction: Anaphylaxis

SEARCH: TEAEs with a PT within the SMQ of Hypersensitivity (narrow scope)

	0001025
Acquired C1 inhibitor deficiency	0081035
Acute generalised exanthematous pustulosis 1	0048799
Administration related reaction 1	0069773
Administration site dermatitis 1	0075096
Administration site eczema 1	0075099
Administration site hypersensitivity 1	0075102
Administration site rash 1	0071156
Administration site recall reaction 1	0075964
Administration site urticaria 1	0075109
Administration site vasculitis 1	0075969
AGEP-DRESS overlap 1	0089003
Allergic bronchitis 1	0052613
Allergic colitis 1	0059447
Allergic cough 1	0053779
Allergic cystitis 1	0051394
Allergic eosinophilia 1	0075185
Allergic gastroenteritis 1	0075308
Allergic hepatitis 1	0071198
Allergic keratitis 1	0057380
Allergic lymphangitis 1	0086007
Allergic oedema 1	0060934
Allergic otitis externa 1	0075072
Allergic otitis media 1	0061557
Allergic pharyngitis 1	0050639
Allergic reaction to excipient 1	0078853
Allergic respiratory disease 1	0063532
Allergic respiratory symptom 1	0063527
Allergic sinusitis 1	0049153
Allergic stomatitis 1	0079554
Allergic transfusion reaction 1	0066173
Allergy alert test positive 1	0075479
Allergy test positive 1	0056352
Allergy to immunoglobulin therapy 1	0074079
Allergy to surgical sutures 1	0077279
Allergy to vaccine 1	0055048

	10070(00
Anal eczema	100/8682
	10002198
Anaphylactic shock	10002199
Anaphylactic transfusion reaction	1006/113
Anaphylactoid reaction	10002216
Anaphylactoid shock	10063119
Anaphylaxis treatment	10002222
Angioedema	10002424
Antiallergic therapy	10064059
Antiendomysial antibody positive	10065514
Anti-neutrophil cytoplasmic antibody positive vasculitis	10050894
Application site dermatitis	10003036
Application site eczema	10050099
Application site hypersensitivity	10063683
Application site rash	10003054
Application site recall reaction	10076024
Application site urticaria	10050104
Application site vasculitis	10076027
Arthritis allergic	10061430
Atopic cough	10081492
Atopy	10003645
Blepharitis allergic	10005149
Blood immunoglobulin E abnormal	10005589
Blood immunoglobulin E increased	10005591
Bone cement allergy	10087325
Bromoderma	10006404
Bronchospasm	10006482
Bullous haemorrhagic dermatosis	10083809
Catheter site dermatitis	10073992
Catheter site eczema	10073995
Catheter site hypersensitivity	10073998
Catheter site rash	10052271
Catheter site urticaria	10052272
Catheter site vasculitis	10074014
Chronic eosinophilic rhinosinusitis	10071399
Chronic hyperplastic eosinophilic sinusitis	10071380
Circulatory collapse	10009192
Circumoral oedema	10052250
Circumoral swelling	10081703
Conjunctival oedema	10010726
Conjunctivitis allergic	10010744
Contact stomatitis	10067510
Contrast media allergy	10066973
Contrast media reaction	10010836

	10011022
Cross sensitivity reaction	10011055
	10011411
Dannia Margan fald	10062018
Dermal filler reaction	10086476
Dermatitis	10012/21
Dermatitis	10012431
Dermatitis alleraie	10012432
Dermatitis atonio	10012434
	10012438
Demantis bullous	10012441
	10012442
	10012455
Dermatitis extoliative generalised	10012456
Dermatitis herpetiformis	10012468
Dermatitis infected	10012470
Dermatitis psoriasiform	10058675
Device allergy	10072867
Dialysis membrane reaction	10076665
Distributive shock	10070559
Documented hypersensitivity to administered product	10076470
Drug eruption	10013687
Drug hypersensitivity	10013700
Drug provocation test	10074350
Drug reaction with eosinophilia and systemic symptoms	10073508
Eczema	10014184
Eczema infantile	10014198
Eczema nummular	10014201
Eczema vaccinatum	10066042
Eczema vesicular	10058681
Eczema weeping	10055182
Encephalitis allergic	10056387
Encephalopathy allergic	10014627
Eosinophilic granulomatosis with polyangiitis	10078117
Epidermal necrosis	10059284
Epidermolysis	10053177
Epidermolysis bullosa	10014989
Epiglottic oedema	10015029
Erythema multiforme	10015218
Erythema nodosum	10015226
Exfoliative rash	10064579
Eye allergy	10015907
Eye oedema	10052139
Eye swelling	10015967
Eyelid oedema	10015993

Face oedema	10016029
Fixed eruption	10016741
Generalised bullous fixed drug eruption	10084905
Giant papillary conjunctivitis	10018258
Gingival oedema	10049305
Gingival swelling	10018291
Gleich's syndrome	10066837
Haemorrhagic urticaria	10059499
Hand dermatitis	10058898
Henoch-Schonlein purpura	10019617
Henoch-Schonlein purpura nephritis	10069440
Heparin-induced thrombocytopenia	10062506
Hypersensitivity	10020751
Hypersensitivity myocarditis	10081004
Hypersensitivity pneumonitis	10081988
Hypersensitivity vasculitis	10020764
Idiopathic urticaria	10021247
Immediate post-injection reaction	10067142
Immune thrombocytopenia	10083842
Immune tolerance induction	10070581
Implant site dermatitis	10063855
Implant site hypersensitivity	10063858
Implant site rash	10063786
Implant site urticaria	10063787
Incision site dermatitis	10073168
Incision site rash	10073411
Infusion related hypersensitivity reaction	10082742
Infusion related reaction	10051792
Infusion site dermatitis	10065458
Infusion site eczema	10074850
Infusion site hypersensitivity	10065471
Infusion site rash	10059830
Infusion site recall reaction	10076085
Infusion site urticaria	10065490
Infusion site vasculitis	10074851
Injection related reaction	10071152
Injection site dermatitis	10022056
Injection site eczema	10066221
Injection site hypersensitivity	10022071
Injection site rash	10022094
Injection site recall reaction	10066797
Injection site urticaria	10022107
Injection site vasculitis	10067995
Instillation site hypersensitivity	10073612

Page 86 of 96

The APTILIAN CONTRACT OF A DECISION	10072(22
Instillation site rash	10073622
	100/302/
	1007(220
	100/6229
	10052098
Kounis syndrome	10069167
Laryngeal oedema	10023845
Laryngitis allergic	10064866
Laryngospasm	10023891
Laryngotracheal oedema	10023893
Limbal swelling	10070492
Lip oedema	10024558
Lip swelling	10024570
Mast cell activation syndrome	10075217
Mast cell degranulation present	10076606
Medical device site dermatitis	10075572
Medical device site eczema	10075575
Medical device site hypersensitivity	10075579
Medical device site rash	10075585
Medical device site recall reaction	10076140
Medical device site urticaria	10075588
Mouth swelling	10075203
Mucocutaneous rash	10056671
Multiple allergies	10028164
Nephritis allergic	10029120
Nikolsky's sign	10029415
Nodular rash	10075807
NSAID exacerbated respiratory disease	10087423
Nutritional supplement allergy	10084049
Oculomucocutaneous syndrome	10030081
Oculorespiratory syndrome	10067317
Oedema mouth	10030110
Oral allergy syndrome	10068355
Oropharyngeal blistering	10067950
Oropharyngeal oedema	10078783
Oropharyngeal spasm	10031111
Oropharyngeal swelling	10031118
Palatal oedema	10056998
Palatal swelling	10074403
Palisaded neutrophilic granulomatous dermatitis	10068809
Palpable purpura	10056872
Patherov reaction	10074332
Penile dermatitis	10087419
Perioral dermatitis	1003/5/1
r errorar dermanno	10034341

Periorbital dermatitis	10087203
Periorbital oedema	10034545
Periorbital swelling	10056647
Pharyngeal oedema	10034829
Pharyngeal swelling	10082270
Polymers allergy	10086347
Procedural shock	10080894
Pruritus allergic	10063438
Puncture site rash	10087940
Radioallergosorbent test positive	10037789
Rash	10037844
Rash erythematous	10037855
Rash follicular	10037857
Rash macular	10037867
Rash maculo-papular	10037868
Rash maculovesicular	10050004
Rash morbilliform	10037870
Rash neonatal	10037871
Rash papulosquamous	10037879
Rash pruritic	10037884
Rash pustular	10037888
Rash rubelliform	10057984
Rash scarlatiniform	10037890
Rash vesicular	10037898
Reaction to azo-dyes	10037973
Reaction to colouring	10037974
Reaction to excipient	10079925
Reaction to flavouring	10082681
Reaction to food additive	10037977
Reaction to preservatives	10064788
Reaction to sweetener	10086454
Rhinitis allergic	10039085
Scleral oedema	10057431
Scleritis allergic	10051126
Scrotal dermatitis	10083260
Scrotal oedema	10039755
Serum sickness	10040400
Serum sickness-like reaction	10040402
Shock	10040560
Shock symptom	10040581
SJS-TEN overlap	10083164
Skin necrosis	10040893
Skin reaction	10040914
Skin test positive	10040934
1	

Solar urticaria	10041307
Solvent sensitivity	10041316
Stevens-Johnson syndrome	10042033
Stoma site hypersensitivity	10074509
Stoma site rash	10059071
Swelling face	10042682
Swelling of eyelid	10042690
Swollen tongue	10042727
Symmetrical drug-related intertriginous and flexural exanthema	10078325
Systemic contact dermatitis	10087943
Tattoo associated skin reaction	10087549
Tongue oedema	10043967
Toxic epidermal necrolysis	10044223
Toxic skin eruption	10057970
Tracheal oedema	10044296
Type I hypersensitivity	10045240
Type II hypersensitivity	10054000
Type III immune complex mediated reaction	10053614
Type IV hypersensitivity reaction	10053613
Urticaria	10046735
Urticaria cholinergic	10046740
Urticaria chronic	10052568
Urticaria contact	10046742
Urticaria papular	10046750
Urticaria physical	10046751
Urticaria pigmentosa	10046752
Urticaria vesiculosa	10046755
Urticarial dermatitis	10082290
Urticarial vasculitis	10048820
Vaccination site dermatitis	10069477
Vaccination site eczema	10076161
Vaccination site exfoliation	10069489
Vaccination site hypersensitivity	10068880
Vaccination site rash	10069482
Vaccination site recall reaction	10076188
Vaccination site urticaria	10069622
Vaccination site vasculitis	10076191
Vaccination site vesicles	10069623
Vaginal ulceration	10046943
Vancomycin infusion reaction	10086737
Vascular access site dermatitis	10085938
Vascular access site eczema	10085939
Vasculitic rash	10047111
Vernal keratoconjunctivitis	10081000
venue keruteen juliet vitis	10001000

H. Lundbeck A/S Confidential
10077117
10077812

Vessel puncture site rash	10077117
Vessel puncture site vesicles	10077813
Vulval eczema	10066273
Vulval ulceration	10047768
Vulvovaginal rash	10071588
Vulvovaginal ulceration	10050181
Vulvovaginitis allergic	10080783

Type II hypersensitivity reaction: Cytokine Release Syndrome (CRS)

SEARCH: TEAEs with the PT 'Cytokine release syndrome'

Type III hypersensitivity reaction: Immune-complex related reactions

SEARCH: TEAEs with a PT within the SMQ Vasculitis (narrow scope), or with the 15 defined PTs

Vasculitis (SMQ):	
Acute haemorrhagic oedema of infancy	10070599
Administration site vasculitis	10075969
Anti-neutrophil cytoplasmic antibody positive vasculitis	10050894
Aortitis	10002921
Application site vasculitis	10076027
Arteritis	10003230
Arteritis coronary	10003232
Behcet's syndrome	10004213
Capillaritis	10068406
Central nervous system vasculitis	10081778
Cerebral arteritis	10008087
Chronic pigmented purpura	10072726
Cogan's syndrome	10056667
Cutaneous vasculitis	10011686
Diabetic arteritis	10077357
Diffuse vasculitis	10012978
Eosinophilic granulomatosis with polyangiitis	10078117
Erythema induratum	10015213
Giant cell arteritis	10018250
Granulomatosis with polyangiitis	10072579
Haemorrhagic occlusive retinal vasculitis	10085070
Haemorrhagic vasculitis	10071252
Henoch-Schonlein purpura	10019617
Henoch-Schonlein purpura nephritis	10069440
Hypersensitivity vasculitis	10020764

Infusion site vasculitis	10074851
Injection site vasculitis	10067995
Kawasaki's disease	10023320
Langerhans' cell histiocytosis	10069698
Lupus vasculitis	10058143
MAGIC syndrome	10078132
Medical device site vasculitis	10076146
Microscopic polyangiitis	10063344
Nodular vasculitis	10029491
Ocular vasculitis	10066926
Polyarteritis nodosa	10036024
Polymyalgia rheumatica	10036099
Pseudovasculitis	10065255
Pulmonary vasculitis	10037457
Radiation vasculitis	10074671
Renal arteritis	10038373
Renal vasculitis	10038546
Retinal occlusive vasculitis	10085059
Retinal vasculitis	10038905
Rheumatoid vasculitis	10048628
Segmented hyalinising vasculitis	10067527
Takayasu's arteritis	10043097
Thromboangiitis obliterans	10043540
Type 2 lepra reaction	10070517
Urticarial vasculitis	10048820
Vaccination site vasculitis	10076191
Vascular purpura	10047097
Vasculitic rash	10047111
Vasculitis	10047115
Vasculitis gastrointestinal	10048319
Vasculitis necrotising	10047124
Viral vasculitis	10056281

Single items PTs:

Glomerulonephritis Glomerulonephritis acute Glomerulonephritis chronic Glomerulonephritis membranoproliferative Glomerulonephritis membranous Glomerulonephritis proliferative Glomerulonephritis rapidly progressive Mesangioproliferative glomerulonephritis Immunotactoid glomerulonephritis Fibrillary glomerulonephritis Membranous-like glomerulopathy with masked IgG-kappa deposits Immune-mediated nephritis Serum sickness Immune complex level increased Type III immune complex mediated reaction

